5.0 Schedule of Assessments and Procedures

	Baseline (Pre-operative clinic visit)	Day 7-14	Post-Treatment safety assessment visit (Day 13 or 14)	Post-treatment sample	Follow-up visit POD 7-14
Tests & Observations					
History	X				X
Age/ECOG PS	X				
Physical Examination	X				X
Pulse, Blood Pressure	X		X		X
Weight/Height	X				
Drug Toxicity Evaluation		X	X		X
Study Drug Calendar		X	X		
EKG	X		X		
Pregnancy test within 2weeks of treatment (urine or serum)	X				
Laboratory Studies					
Ca, Mg, K, Cr, PT, PTT, Bilirubin, AST, ALT, Alk Phos, CBC	X				
Ca, Mg, K, platelets			X		
Treatment					
Placebo/Vandetanib 300 mg daily		X			
Staging Evaluations					
Pathologic Tumor Size				X	
Histology	X			X	
Tumor markers ¹	X			X	
Elston-Ellis Grade ²	X			X	
Lymph node status ³	X (CLINICAL)			X (PATHOLOGIC)	

Note: Staging determinants can be obtained on the baseline or post-treatment sample. They do not need to be obtained on both, but should reflect the final conclusions of the pathologist.

¹ Tumor markers are Estrogen Receptor, Progesterone Receptor and Her2/neu. See Section 9.2.

² Eliston-Ellis Grade is a pathological term for tumor aggression.

³ Lymph node status will be recorded in accordance with preoperative (clinical) and postoperative (pathologic) staging.

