The first dose of Vandetanib tablets will be taken only after all the assessments assigned have been performed. Patients should take study drug in the morning. If a patient inadvertently misses a dose and the next dose is in 12 hours or more, the patient should take the missed dose immediately and the next dose at the normal time. If it is less than 12 hours before the next dose, the patient should take the next dose at the normal time and the missed dose should not be taken. The missed dose must be documented in the CRF, where appropriate, with a comment indicating the patient missed the dose. The dose of study treatment may be repeated if vomiting occurs within 30 minutes of taking the study treatment. If vomiting occurs after 30 minutes of taking the study treatment, the dose will not be repeated.

Labels will be prepared in accordance with Good Manufacturing Practice (GMP) and local regulatory guidelines. The labels will fulfill GMP Annex 13 requirements for labeling.

Information on the bottle labels for Vandetanib will indicate the study number, contents, caution, and storage conditions and will have blank spaces for the patient number, visit number, and dispensing date (to be written in by the site personnel at the center at the time of dispensing). Instruction that study drug should be taken as directed will be included on the label. Patients will be supplied with a study participation card where the dosing instruction will be described for a patient by Investigator or delegate. All study drugs should be kept in a secure place under appropriate storage conditions

Administration

Subjects will be asked to take Vandetanib as a single oral daily dose of 300 mg or placebo. Patients will discontinue the drug and be removed from the study for toxicity. A patient may withdraw from the study at any time for any reason without prejudice for future treatment. Patients will be removed from the study for failure to comply with greater than 80% of scheduled doses.

Toxicity

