10.0 Removal of Subjects from Protocol Therapy

10.1 Duration of Treatment

Subjects will continue vandetanib or placebo up to and including the morning of surgery for a total of 7 to 14 days. The time frame from preoperative clinic visit until definitive surgery will be a minimum of 2 weeks and the maximum of 4 weeks. Subjects with an adverse reaction of CTCAE grade III or higher will discontinue the study drug. Subjects can voluntarily discontinue the drug at any time during the trial, be removed from the drug at the discretion of their treating physician, or be discontinued by the study investigators. In previous trials with vandetanib, surveillance labs and toxicity assessment has been performed at two weeks of treatment, which will be done in this trial with the preoperative safety assessment. Because subjects will have already discontinued the study drug at that time it will not be possible to discontinue the study drug early based on that assessment. Due to the short duration of treatment in this trial and the low incidence of adverse reactions over that time frame in previous phase I and II trials we do not expect a significant number of severe adverse reactions. Subjects will be evaluated for study withdrawal if noncompliant with requirement for therapy, or if they are experiencing drug related toxicity. If the date of surgery is unexpectedly changed after initiation of treatment, the patient will continue treatment, including the morning of surgery, for not more than 28 total days.

10.2 Extraordinary Medical Circumstances:

If at any time the constraints of this protocol are detrimental to the subject's health and/or the subject no longer wishes to continue protocol therapy, remove the subject from the protocol treatment. In this event:

- Document the reason(s) for ending treatment on the follow-up form.
- The primary outcomes of response of down regulation of Ki-67 and secondary outcomes of evaluation of tumor markers in the baseline and endpoint tissue samples will be analyzed unless the subject withdraws consent to do so.

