11.2.2 Assessment of Risk Level

The Data Safety Monitoring Plan (DSMP) can be found in Appendix 5 of this protocol.

This investigation involves a risk-level 3 procedure, in a population that should not be at any increased risk for complications.

11.2.3 Assessing Toxicity:

Toxicity will be graded according to NCI’s Common Toxicity Criteria (CTCAE v4). The investigator will determine relationship of toxicity to the investigational drug as unrelated, unlikely related, possibly related, probably related, or definitely related using standard criteria for clinical trials. All grades of toxicity will be noted and reported as directed in Table I: Clinical Data Update System (CDUS) Guidelines for Routine Adverse Event Reporting.

Patients who experience a CTCAE (version 4) Grade 3 or 4 toxicity that is considered related to Vandetanib will have their study drug stopped. If a patient discontinues treatment, safety follow-up visits will be performed according to the schedule of assessments and procedures. In addition, a 30 day follow up visit will occur if AEs have not resolved by the time of the post op safety visit. SAEs and study drug-related AEs must be followed until resolution unless in the Investigator’s opinion, the event is unlikely to resolve due to the patient’s underlying condition.

Cardiac toxicity - QTc prolongation

Electrocardiograms will be evaluated by suitably qualified personnel for the presence of QTc prolongation or other abnormalities, in particular, any changes in the T-wave morphology that would suggest a higher likelihood for the development of any arrhythmia. Any clinically significant abnormal findings or QTc prolongations will be recorded as AEs.

In addition to scheduled ECG, additional ECGs should also be performed in the event of QTc prolongation, both during and post the prolongation period.

- During the QTc prolongation period: For a single QTc value of >500 ms, Vandetanib must be withheld and patients will be removed from the study. Electrocardiograms will be followed at least once per week (done at the same day each week) along with electrolytes, until QTc falls \leq 480 ms.

Gastrointestinal toxicity

Nausea, vomiting, or both may be controlled with anti-emetic therapy. The use of somatostatin or a somatostatin analogue is allowed to control diarrhea.

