Diarrhea should be treated with standard medications to avoid dose modification or interruption, if possible. Electrolyte supplementation with regular laboratory monitoring should be used, when appropriate, to maintain electrolytes within normal limits and prevent an increased risk of QTc prolongation.

If CTCAE Grade 3 or 4 diarrhea develops, patients will be removed from the study. Any electrolyte imbalance must be promptly corrected since hypokalemia and hypomagnesaemia are potential risk factors for drug-induced arrhythmia.

Cutaneous toxicity

It is strongly recommended that all patients follow a program of sun protective measures (wearing additional clothing and/or sunscreen) while receiving study treatment and for 3 to 4 weeks after discontinuing study treatment. The aim is to reduce the risk of development of skin rash, or minimize the severity of skin rash, and to minimize the requirement for dose reduction of study therapy.

If a patient develops a skin rash, the following actions are recommended to the Investigator for the management of this reaction:

- A variety of agents can be used to manage skin rashes. These include mild to moderate strength steroid creams or systemic glucocorticoids, either topical or systemic antibiotics, topical or systemic antihistamines, and occasionally retinoid creams.
- The rash should be graded as soon as possible according to the CTCAE cutaneous toxicity criteria.
- If a rash of CTCAE Grade 2 or higher is detected, immediate symptomatic treatment should be provided.
- If a rash of CTCAE Grade 3 or 4 is detected, patients will be removed from the study

Hypertension

Patients who develop CTCAE Grade 3 hypertension may continue on therapy if blood pressure is controlled on increased anti-hypertensive medication (to CTCAE Grade 1 or baseline). If blood pressure cannot be stabilized with increased anti-hypertensive medication, patients will be removed from the study.

Patients with CTCAE Grade 4 hypertension must be removed from the study.

11.2.4 Adverse Event Reporting:

Table I:

Clinical Data Update System (CDUS) Guidelines for Routine Adverse Event Reporting

Attribution	Adverse Event				
	Grade 1	Grade 2	Grade 3	Grade 4	Grade 5
Unrelated	Not required	Not required	CRSO	CRSO	CRSO
Unlikely	Not required	Not required	CRSO	CRSO	CRSO
Possible	CRSO	CRSO	CRSO	CRSO	CRSO
Probable	CRSO	CRSO	CRSO	CRSO	CRSO
Definite	CRSO	CRSO	CRSO	CRSO	CRSO

Reports are collected by the CRSO or DSMB and communicated to the DSMC

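### Related Grade 3 hypertension must stop study drug under Section 10.1 and the general rule of 11.2.3, but may continue under the hypertension paragraph of 11.2.3

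*Combined protocol and SAP*

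**What the plan says.** Four statements in the protocol bear on a patient who develops Grade 3 hypertension.

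- Section 10.1 (Duration of Treatment): "Subjects with an adverse reaction of CTCAE grade III or higher will discontinue the study drug". It names no exception and does not refer to 11.2.3.
- Section 11.2.3 (Assessing Toxicity), general rule: "Patients who experience a CTCAE (version 4) Grade 3 or 4 toxicity that is considered related to Vandetanib will have their study drug stopped". It names no exception either.
- Section 11.2.3, Hypertension: "Patients who develop CTCAE Grade 3 hypertension may continue on therapy if blood pressure is controlled on increased anti-hypertensive medication", where controlled means back to CTCAE Grade 1 or baseline. It goes on: "If blood pressure cannot be stabilized with increased anti-hypertensive medication, patients will be removed from the study". Grade 4 hypertension leads to removal.
- Section 7.1 (Administration): "Patients will discontinue the drug and be removed from the study for toxicity". No grade is given.

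On monitoring, the row "Pulse, Blood Pressure" in Section 5.0 is marked at baseline, at the post-treatment safety visit (labelled Day 13 or 14) and at the follow-up visit 7 to 14 days after surgery. It is empty in the Day 7-14 dosing column. Section 6.0 puts the safety visit on the day before or the morning of surgery, with the last dose that morning. Section 10.1 lets dosing run to at most 28 days if surgery is moved.

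**The concern.** For one specific event, two rules say stop and a third says the patient may go on. No text says which prevails. This is a stopping rule in a blinded trial of a drug for which the protocol lists hypertension among effects seen in more than 10% of patients, so the event is foreseeable.

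The first consequence is for patient safety, because whether dosing continues would depend on which section the investigator reads. The second is for oversight. The audits in Section 11.1 and Appendix 5 check compliance with the protocol, and either action could be called compliant or a deviation. The third is for exposure. The Ki-67 comparison rests on a short course, and patients handled under different rules would contribute tumor pairs after different numbers of doses.

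The schedule is a separate problem. The permission to continue depends on observing that pressure came under control, and the planned assessments do not provide a reading at a time when that could be shown.

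**Working it through.** No power or sample-size figure in the plan is at issue. The check compares the rules case by case and then counts doses.

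**Step 1. Apply each rule to the same patient.**

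| Case | 10.1 | 11.2.3 general rule | 11.2.3 hypertension | 7.1 |
|---|---|---|---|---|
| Grade 3, related, controlled | stop drug | stop drug | may continue | discontinue and remove (no grade) |
| Grade 3, related, not stabilized | stop drug | stop drug | remove | discontinue and remove |
| Grade 4, related | stop drug | stop drug | remove | discontinue and remove |
| Grade 3, judged unrelated, controlled | depends on what an adverse reaction covers | does not apply | may continue | depends on what toxicity covers |

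In the second and third rows all the rules end dosing. The first row is a direct contradiction. The fourth is uncertain, because the general rule is limited to related toxicity and Section 10.1 speaks of an adverse reaction. The firm claim therefore concerns related Grade 3 hypertension that is brought under control.

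**Step 2. Doses left after the scheduled blood-pressure reading.** Doses left = last dosing day minus visit day. Inputs are from Sections 5.0, 6.0 and 10.1.

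- 14-day course: 14 − 13 = 1 with a Day 13 visit; 14 − 14 = 0 with a Day 14 visit once that morning's dose is taken.
- 7-day course, visit placed by Section 6.0: 7 − 6 = 1 on the day before surgery; 7 − 7 = 0 on the morning of surgery once the dose is taken. The Day 13 or 14 label does not fit this course.
- Surgery postponed to the 28-day limit, with a reading on Day 13 or 14: 28 − 13 = 15 or 28 − 14 = 14.

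In the planned course at most one dose follows the reading. That leaves no time to increase medication, confirm control and continue. Section 10.1 itself says this assessment comes too late to stop the drug early. It also treats the drug as already finished by then, whereas Section 6.0 allows the visit on the day before the last dose.

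**Step 3. Does a stop at that visit breach the 80% dose rule of Section 6.0?**

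- Minimum doses: 0.8 × 7 = 5.6, so 6 are needed and 1 may be missed; 0.8 × 14 = 11.2, so 12 are needed and 2 may be missed.
- Missing only the final dose leaves 6/7 = 86% or 13/14 = 93%. Both exceed 80%.

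A stop at the scheduled visit does not by itself remove the patient for non-adherence. Only an earlier stop, after an unscheduled reading, could do so.

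**Step 4. Number of patients.** The only frequency given is more than 10% for hypertension of any grade, with no exposure duration and no Grade 3 share. A count cannot be derived from it.

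**The case against.** The best defence is that the hypertension paragraph is a specific exception to the general rule of its own section. That is a natural reading inside 11.2.3, which moves from a general sentence to paragraphs on particular toxicities, and it weakens the conflict there. It does not settle the matter. No text states the exception, and the neighbouring paragraphs on diarrhea and rash both remove patients at Grade 3 or 4, as the general rule would lead one to expect. Nor does the reading reach Section 10.1, which is a separate rule without a carve-out.

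It can also be said that blood pressure during dosing is not ruled out. This stands. The schedule marks a drug toxicity evaluation and the study drug calendar in the dosing column, and nothing prohibits unscheduled readings. The supportable statement is that no blood-pressure reading is scheduled during dosing before the safety visit.

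Several stronger inferences are tempting, and the documents do not support them.

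- *The late reading causes the contradiction.* It does not. The contradiction lies in the rule texts, and a late reading makes it less likely to surface at a scheduled visit.
- *Affected patients can be counted, for instance from 40 × 10% = 4 and an assumed Grade 3 share.* The share is not given. The 10% figure has no duration attached, uncontrolled hypertension is an exclusion, and Sections 7.1 and 10.1 expect little toxicity over so short a course. Even 4 is not a safe lower bound.
- *The losses use up a stated part of the margin of 5 per arm between 40 enrolled and 35 evaluable.* This inherits the unknown count and assumes that every stopped patient is lost. Section 10.2 says Ki-67 will still be analyzed after treatment ends for health reasons unless consent is withdrawn. Section 12 does allow for ineligibility through missed doses, so a loss is possible but not established.
- *All affected patients are on vandetanib.* The trial is blinded and the rules act on placebo patients too.

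**Conclusion.** The concern holds in this form: for Grade 3 hypertension considered related to study drug and then controlled, Section 10.1 and the general rule of 11.2.3 require a stop, while the hypertension paragraph permits continuation. Section 7.1 adds an ungraded rule that does not resolve the conflict. This is an error in the operative text and needs no assumption about rates.

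The schedule gap is a second, independent finding. In the planned 7 to 14 day course at most one dose follows the scheduled reading, so the condition for continuing could be met only through unscheduled readings, or when surgery is postponed within the 28-day limit.

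The number of patients affected cannot be computed, and it may be zero. A reader might infer a measurable loss of power or a breach of the adherence rule at the safety visit. The first lacks inputs, and Step 3 shows that the second does not follow. The point should be corrected because it concerns a stopping rule and is cheap to repair. It does not show that the primary comparison is compromised.

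**What to change.** 1. Reconcile Section 7.1 (Administration), Section 10.1, and the general rule and hypertension paragraph of Section 11.2.3 so that Grade 3 hypertension has one stated outcome, with matching cross-references. Which outcome applies is for the sponsor's clinicians to decide; this review takes no position.
2. Make the schedule in Section 5.0 consistent with the rule that is kept. If the rule depends on blood pressure being controlled on drug, the schedule should show where that is documented. The Day 13 or 14 label of the safety visit should also be squared with Section 6.0 for a 7-dose course.
3. Record on the case report form, for each such event, the grade, the attribution, and whether study drug was continued or stopped, so that exposure can be described by arm.

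The cost is a wording amendment to three sections, a matching check of the schedule table and one case report form item. Sample size and analysis method do not change.

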12.0 Statistical Analysis

In this study, women will be enrolled after core breast biopsy demonstrates invasive breast cancer. Baseline tissue sample will be obtained on study participants, after which, subjects will take Vandetanib or placebo until the time of a definitive surgical procedure, at which point the resection specimen will serve as a paired tissue sample. In vivo response Vandetanib will be assessed through analyses of the change in tissue levels of KI67, TUNEL, and changes in activation of ERK1/2, AKT, and mTOR and compared to placebo treated patients. All data points will be evaluated as paired continuous data points.

Descriptive statistics (means, medians, standard deviations, percentages, and confidence intervals) will be reported for all baseline and follow-up variables as well as for their changes over time. Statistical comparisons of the changes will be performed with paired t-test for continuous variables. Power analysis for comparisons of

continuous variables was based on published results for Ki-67 [20]— the only readily available results for the proposed treatment and study population. Based on a published standard deviation of 10%, the planned enrollment of 35 subjects will ensure 90% power to detect a decrease of 5% in Ki-67. The power drops to 82% if a two-sided alternative is considered. We will enroll 40 patients in each arm to account for non-compliance and withdrawal.

With a total of 70 evaluable patients (i.e. 35 in control and 35 in treatment group), we can achieve 70% power to detect 6% difference in Ki-67 between the two arms, from the null hypothesis that both arms have equal expression of Ki-67. In this case, we operate under the assumption that both arms have similar standard deviation of 10%, that the significance level is 5%, and that a two-sided two-sample t-test has been used. The power is 80% if a one-sided two-sample t-test is used under the same assumptions. We will enroll 80 patients (40 per arm) to account for potential patient dropouts and ineligibility for analysis due to missed doses.

Power in subgroup comparisons is likely to be low and, thus, the results are most useful for generating hypotheses to be tested in future studies. All statistical tests will be one-sided and assessed for significance at the 5% level.

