2.0 Study Objectives

- 2.1 Determine the change in Ki-67 expression on paired samples obtained before and after Vandetanib treatment.
- 2.2 Compare TUNEL levels and phosphorylation specific levels of ERK1/2, AKT, and mTOR levels in paired samples obtained before and after Vandetanib treatment.
- 2.3 Evaluate any differences in analyses 2.1 and 2.2 based on level of RET expression as well as between ER-positive and ER-negative tumors.

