9.0 Criteria for Response

The primary study end point will be down regulation of proliferative index measured by Ki-67 expression.

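### Section 12 promises a comparison with placebo, but the only test it assigns to the marker changes is a within-arm paired t-test, and no test is named as deciding the Ki-67 primary endpoint

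*Combined protocol and SAP*

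**What the plan says.** The statements that bear on the deciding test are in three places.

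- **Section 12.0, intent.** Changes in Ki-67, TUNEL and the phosphorylation markers will be assessed "and compared to placebo treated patients".
- **Section 12.0, data structure and test.** "All data points will be evaluated as paired continuous data points". Then: "Statistical comparisons of the changes will be performed with paired t-test for continuous variables". No other sentence assigns a test to the changes.
- **Section 12.0, first power statement.** With a published SD of 10%, "the planned enrollment of 35 subjects will ensure 90% power to detect a decrease of 5% in Ki-67", falling to 82% two-sided. This is a one-group calculation.
- **Section 12.0, second power statement.** With 35 evaluable patients per arm and SD 10% in each, power for a 6% difference between arms is 70% for a two-sided two-sample t-test and 80% one-sided. The difference is measured "from the null hypothesis that both arms have equal expression of Ki-67".
- **Section 12.0, closing rule.** All tests are one-sided at 5%.
- **Section 2.0.** Objective 2.1 reads "Determine the change in Ki-67 expression on paired samples obtained before and after Vandetanib treatment". Objective 2.2 reads "Compare TUNEL levels and phosphorylation specific levels of ERK1/2, AKT, and mTOR levels in paired samples obtained before and after Vandetanib treatment". Neither mentions placebo.
- **Section 9.0.** "The primary study end point will be down regulation of proliferative index measured by Ki-67 expression". No comparator and no test are given.

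**The concern.** Under Section 7.1, patients are randomised in groups of eight without stratification, so a vandetanib patient has no matched placebo partner. The assigned paired test can therefore only be a before/after test within an arm, which is not the placebo comparison promised in the same section. An analyst who followed the test sentence and Objective 2.1 literally would base the primary result on the vandetanib arm alone. An analyst who followed the second power paragraph would compare the arms. Both could claim to have followed the plan, and they could reach opposite conclusions.

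The choice matters because the two samples differ in kind: by Section 1.3, baseline is a diagnostic core biopsy and endpoint a surgical resection. Any systematic difference between these sample types is part of every within-arm change. A common fall would be counted as drug effect, and a common rise would hide one. Only a between-arm contrast cancels it, which is a main reason for having a placebo arm.

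**Working it through.** **Inputs from Section 12.0:** 35 evaluable per arm; SD 10; effects of 5 (one group) and 6 (two arms); 5% level. **Assumptions of this check, not in the documents:** the size and direction of a common shift (1 to 3 percentage points either way) and the baseline-to-endpoint correlation ρ (0.3 to 0.7), with equal variances at the two time points. Power is from the noncentral t distribution.

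**1. The plan's own figures.**
- One group: ncp = (5/10)·√35 = 2.958, df 34. Power is 89.5% one-sided and 82.0% two-sided (plan: 90%, 82%).
- Two arms: ncp = (6/10)·√(35/2) = 2.510, df 68. Power is 80.0% one-sided and 69.7% two-sided (plan: 80%, 70%).

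The arithmetic is right in both cases, but the hypotheses differ. For the same 5 points, the between-arm test has ncp = (5/10)·√(35/2) = 2.092 and power of only 66.5% one-sided (54.1% two-sided).

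**2. Common shift, no drug effect.** Vandetanib-arm paired test, SD of change 10, one-sided 5%, ncp = (shift/10)·√35:

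| Shift common to both arms | 1 point | 2 points | 3 points |
|---|---|---|---|
| Fall: chance of a significant result | 14.3% | 31.4% | 53.8% |
| Rise: chance of a significant result | 1.3% | 0.25% | 0.04% |

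The two-sample t-test on change holds its level because the shift cancels. In simulation (40,000 replicates) it rejected in 4.8% to 5.1% of trials in all six cases.

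**3. Common rise, true drug effect of 6 points.** The paired test sees 6 minus the rise. Its power is 96.7% with no shift, and 89.5%, 75.0% and 53.8% with a rise of 1, 2 and 3 points. Between-arm power stays at 80.0%.

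**4. What the SD of 10 refers to.** Section 12.0 does not say whether it is the SD of change or of a single measurement. If single, SD of change = 10·√(2(1−ρ)). If of change, single-measurement SD = 10/√(2(1−ρ)). ANCOVA residual SD is 10·√(1−ρ²) in the first case and 10·√((1+ρ)/2) in the second, with df 67. Between-arm power for 6 points, 35 per arm, one-sided (two-sided in brackets):

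| Analysis | Meaning of SD 10 | ρ = 0.3 | ρ = 0.5 | ρ = 0.7 |
|---|---|---|---|---|
| t-test on change | change | 80% (70%) | 80% (70%) | 80% (70%) |
| t-test on endpoint only | change | 90% (83%) | 80% (70%) | 61% (48%) |
| ANCOVA | change | 92% (87%) | 89% (82%) | 85% (77%) |
| t-test on change | single measurement | 68% (55%) | 80% (70%) | 94% (89%) |
| t-test on endpoint only | single measurement | 80% (70%) | 80% (70%) | 80% (70%) |
| ANCOVA | single measurement | 83% (74%) | 89% (82%) | 97% (93%) |

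The stated 80%/70% therefore holds only if 10 is the SD of the variable actually tested. The null of equal expression, set beside a plan to analyse changes, leaves that variable undefined.

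**The case against.** The best defence is that a between-arm test was plainly intended. The trial is randomised and placebo-controlled, Section 12.0 speaks of comparison with placebo, and its second power paragraph gives effect, SD, level and a two-sample t-test for 35 per arm. On that reading the paired test is for within-patient change and the two-sample test for the arms. The sentence about paired data may only describe the data structure, and equal expression may be loose shorthand.

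The harm is also conditional. It needs the paired test to be treated as decisive and a systematic biopsy-to-resection shift to exist. The documents report no such shift, Section 9.1 has the blocks analysed and interpreted at one institution, and Section 9.2 uses formalin-fixed, paraffin-embedded tissue throughout. Neither power figure is miscalculated, and both lead to 40 enrolled per arm. ANCOVA is a preference, not a necessity.

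Much of this stands. Intent can be inferred, the shift sizes and correlations are assumptions, and a two-sample t-test on change would be enough. What does not fall away is that intent is never turned into a rule. The two-sample test is not assigned to the changes or to the primary endpoint, and the one test that is assigned cannot make the promised comparison.

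**Conclusion.** The concern holds and must be fixed before the primary analysis. This is a fault of specification: all four stated power figures reproduce. As written, a within-arm primary result that ignores the placebo arm complies with the plan. Under the illustrative assumptions, a shared shift of 1 to 3 points moves that test's false-positive rate to between 14% and 54% if it is a fall. If it is a rise, power for a true 6-point effect drops from 97% to between 89.5% and 54%. A between-arm test of change is unaffected. The 90% power figure belongs only to the within-arm test. That the deciding test is missing depends on none of these assumptions; only the illustrated size does.

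**What to change.** In Section 12.0:

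1. Name one between-arm primary analysis of Ki-67 and report the vandetanib-minus-placebo difference with a confidence interval. A two-sample t-test on change is sufficient. ANCOVA of endpoint Ki-67 on arm with baseline Ki-67 as covariate is preferable, since it has more power than either simpler test across the assumed correlations.
2. Use the same model for TUNEL, pERK1/2, pAKT and p-mTOR, and keep paired t-tests as within-arm description.
3. State the null for the quantity tested, and say whether the SD of 10 is for change or a single measurement.
4. Label 90%/82% as within-arm and make the between-arm power the operative figure.

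In Section 2.0, reword Objectives 2.1 and 2.2 as comparisons of change between vandetanib and placebo.

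**Cost:** wording and minor analysis work. Evaluable patients (35 of 40 per arm assumed in the plan) already provide both samples, so no new data or patients are needed. The price is a less favourable headline: 80% one-sided power for 6 points in place of 90% for 5.
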